3. SUMMARY

- **Title of the project:** ULTRASOUND-GUIDED PERCUTANEOUS TRANSVERSE CARPAL LIGAMENT SECTION VS OPEN SURGERY FOR THE SURGICAL TREATMENT OF CARPAL TUNNEL SYNDROME (CTS).

- **Principal investigator.**

- [name]. F.E.A. Orthopaedic Surgery and Traumatology. University Hospital Complex of Vigo.

- **Centres where the study is planned to be carried out.** University Hospital Complex of Vigo

- **Design.** Prospective observational cohort study.

- **Main and secondary objectives:** To analyze the functional outcome of patients operated on for carpal tunnel syndrome (CTS) in a percutaneous ultrasound-guided manner and compare it with the results obtained by open surgery.

- **Primary endpoint:** Clinical and functional improvement using a specific questionnaire for CTS: Boston Carpal Tunnel Syndrome Questionnaire (BCTQ).

- **Population under study and total number of patients:** Patients from the CHUVI Health Area who have been diagnosed with Carpal Tunnel Syndrome and are going to undergo surgery at the centre from 1 February 2021 to 31 December 2021 by doctors

specialising in Orthopaedic Surgery and traumatology belonging to the CHUVI Upper Limb Unit.

- **Duration of patient enrollment:** From January 1, 2021 to January 31, 2024 (or until the calculated sample size is completed).
- **Calendar and expected date of completion of the study:** February 2024 end of collection; between April and May 2024 analysis and dissemination of results.

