6. SPECIFIC AND SECONDARY OBJECTIVES OF THE STUDY

Main objective:

To analyze the functional results of the surgical treatment of CTS using percutaneous ultrasound-guided technique and to compare them with the results obtained by open surgery with a palmar incision.

Secondary objective:

To analyze the presence of complications (scar pain, pillar pain) and the pre- and postoperative difference in manual grip strength (measured with a JAMAR manual dynamometer) of surgical treatment of CTS using percutaneous ultrasound-guided technique and compare them with the results obtained by open surgery with a palmar incision.

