7. DESIGN AND METHODS

Design:

Prospective observational cohort study.

Study population:

Patients in the CHUVI Health Area who have been diagnosed with CTS by a specialist in Orthopaedic Surgery and Traumatology at that centre, have undergone surgery for this pathology from 1 January 2021 to 31 January 2024, and meet the inclusion and exclusion criteria.

- Inclusion Criteria:

- 1.- Patient diagnosed with CTS by clinical examination and confirmed by complementary test (Electromyogram).
- 2.- Patients over 18 years of age.
- 3.- Patients who belong to the CHUVI Health Area.
- 4.- Patients with the capacity to consent and who agree to participate by signing the informed consent.
- 5.- Follow the guidelines and reviews set forth in the Consultation.

- Exclusion Criteria:

- 1- Patient who has previously undergone surgery for the same pathology in the same hand (recurrence).
- 2.- Patient incapacitated or unable to follow guidelines indicated by the Physician.
- 3.- Patient with associated pathology in the same hand for which he/she is going to be operated on in the same surgical act.
- 4- Patients with the presence of associated synovitis at the level of the flexor tendons of the hand to be treated.

- Sample size calculation.

Based on the study published by Kim et al²³, who studied the minimum clinically important difference (MCID) for the Boston Carpal Tunnel Syndrome Questionnaire²², and accepting an alpha risk of 0.05 and a beta risk of less than 0.2 in a bilateral contrast,

98 subjects in the first group and 98 in the second group are needed to detect a difference equal to or greater than 0.94 units. The common standard deviation is assumed to be 1. A follow-up loss rate of 10% has been estimated.

Procedure

Patients from the CHUVI Health Area diagnosed with the explained pathology, who meet the inclusion and exclusion criteria, and who are going to undergo surgery at the CHUVI by specialist doctors from the Orthopaedic Surgery and Traumatology Service belonging to the Upper Limb Unit, will be recruited. These patients will be informed of their pathology, and after signing the informed consent, surgery will be performed in the two proposed ways:

-Procedure A: ultrasound-guided percutaneous surgery.

-Procedure B: open surgery through a short palmar incision.

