These two forms of surgical treatment are approved and used in our Service. The assignment to one or another surgical technique will be made based on the criteria of the physician who diagnoses the patient, as he or she does in his or her usual clinical practice, once the patient's clinical characteristics, pathology, and preferences have been heard.

Data will be collected from the patients included in the study in the preoperative consultation, intraoperatively and in the revision consultations that are usually carried out for this pathology 2 weeks after surgery, 6 weeks and 3 months.

In the preoperative consultation, the following will be collected:

- 1.- Grip strength of the hand measured with JAMAR manual dynamometer.
- 2.- Score of the specific questionnaire for the pathology of CTS: Boston Carpal Tunnel Syndrome Questionnaire²² (ANNEX 1).

Surgery will include:

- 1.- Time of surgical intervention
- 2.- Use or not of an ischemia cuff to perform surgery.

In the 2-week postoperative consultation, the following will be assessed:

- 1.- State of surgical wound.
- 2.- Presence of skin infection or other complication.
- 3.- Presence of pillar pain.
- 4.- Absence or presence of CTS (paresthesias or pain in the territory of the median nerve).

In the consultations that will be carried out 6 weeks and 3 months after surgery, the following will be assessed:

- 1.- Surgical incision status.
- 2.- Presence of skin infection or other complication.
- 3.- Presence of pillar pain.
- 4.- Absence or presence of CTS (paresthesias or pain in the territory of the median nerve)
- 5.- Grip strength of the hand measured with a JAMAR manual dynamometer.
- 6.- Score of the specific questionnaire for the pathology of CTS: Boston Carpal Tunnel Syndrome Questionnaire²² (ANNEX 1).

Data recording and management.

Potential candidates who meet the main characteristic of the study will be offered informed consent. Once the consent has been signed, a list of patients who meet the inclusion criteria and none of the exclusion criteria will be created.

The principal investigator ([name] [name]) will be responsible for the collection and custody of the data and will ensure that the pseudonymisation of the participants is maintained. These will be identified through a code in the CRD and in the electronic database, all their information being associated with this code and not with their personal data.

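### Data collection is due to end in February 2024, before the last 6-week and 3-month BCTQ visits that the surgery window allows; one summary line also gives a different surgery window

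*Protocol*

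**What the plan says.** **Calendar.** Section 3 of the protocol gives, as the expected timetable, "February 2024 end of collection; between April and May 2024 analysis and dissemination of results". Section 9 instead has a single block for analysis and dissemination, running from February to May 2024.

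**Recruitment and surgery.** The enrolment line in section 3 reads "From January 1, 2021 to January 31, 2024 (or until the calculated sample size is completed". The study population in section 7 is patients who "have undergone surgery for this pathology from 1 January 2021 to 31 January 2024". Section 9 gives the same inclusion period, January 2021 to 31 January 2024. The population line in section 3 differs: it describes patients "going to undergo surgery at the centre from 1 February 2021 to 31 December 2021".

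**Follow-up.** Section 7 collects data before surgery, during surgery and "in the revision consultations that are usually carried out for this pathology 2 weeks after surgery, 6 weeks and 3 months". The 2-week list covers the wound, infection or other complications, pillar pain and persisting CTS symptoms. The list that includes grip strength and the BCTQ is introduced by "In the consultations that will be carried out 6 weeks and 3 months after surgery, the following will be assessed". The BCTQ is the primary endpoint (section 3), and the change in grip strength belongs to the secondary objective (section 6).

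**The concern.** The closing date has to allow for the follow-up of the last patient operated on. Here the last permitted surgery is on 31 January 2024 and collection is expected to end in the following month. That leaves room only for the 2-week visit, which records neither the primary endpoint nor grip strength. If the February date is followed, late recruits lose scheduled BCTQ and grip measurements for no reason other than the closing date.

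The analysis periods raise the same question, since both open before the last possible 3-month visit.

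The 2021-only line is a separate defect. It gives a recruitment period that the rest of the protocol contradicts.

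**Working it through.** **Inputs**

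| Item | Value | Source in protocol |
|---|---|---|
| End of collection | February 2024; latest reading 29 February | Section 3, calendar |
| Last surgery date | 31 January 2024 | Section 7, study population |
| Visits with postoperative BCTQ and grip strength | 6 weeks (42 days) and 3 months | Section 7, procedure |
| Planned patients | 98 + 98 = 196 | Section 7, sample size |
| Accrual rate | Not given; even accrual from 1 January 2021 assumed | – |

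**Step 1: last visits for surgery on 31 January 2024**

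- 2 weeks: + 14 days = 14 February 2024, inside February.
- 6 weeks: + 42 days = 13 March 2024, 13 days after 29 February.
- 3 months: 30 April 2024 (month-end), 61 days after 29 February. Counted as 13 weeks it is 1 May.

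**Step 2: last surgery dates that fit a close on 29 February 2024**

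- For the 6-week visit: 29 February − 42 days = 18 January 2024.
- For the 3-month visit: 30 November 2023 + 3 months = 29 February 2024, because there is no 30 February. Counting back 3 calendar months gives 29 November and counting back 13 weeks gives 30 November, so the convention matters by one day.
- 29 February is the reading most favourable to the plan. With a close on 1 February 2024 the limits would be 21 December 2023 (6 weeks) and 1 November 2023 (3 months).

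Surgery from 1 December 2023 to 31 January 2024 (31 + 31 = 62 days) therefore yields no 3-month BCTQ by the close. Surgery from 19 to 31 January 2024 (13 days) yields no postoperative BCTQ at all.

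**Step 3: how many patients**

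Affected = 196 × (affected days ÷ days of accrual).

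| Enrolment complete on | Days from 1 January 2021 | Per month | No 3-month BCTQ | No postoperative BCTQ |
|---|---|---|---|---|
| 30 November 2023 | 1,064 | 196/35 = 5.6 | 0 | 0 |
| 31 December 2023 | 1,095 | 196/36 = 5.4 | 196 × 31/1,095 ≈ 5.5 (2.8%) | 0 |
| 31 January 2024 | 1,126 | 196/37 = 5.3 | 196 × 62/1,126 = 10.8 (5.5%) | 196 × 13/1,126 = 2.3 (1.2%) |

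**Step 4: the 2021-only line**

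1 February to 31 December 2021 is 334 days, and 334/1,126 = 29.7% of the window stated elsewhere. Under that line the last 3-month visit would fall on 31 March 2022 and there would be no overrun. However, the line conflicts with the enrolment line of the same summary and with sections 7 and 9.

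**The case against.** The strongest reply is that no stated rule causes any loss. The February date is only an expected one, enrolment may stop as soon as the sample size is reached, and visits are fixed for each patient. Nothing in the protocol says that a visit after February is cancelled or its data discarded. This stands as a limit on the consequence: loss follows only if surgery continues past about 30 November 2023 and February is applied as a cut-off. It does not make the dates compatible. A calendar should be workable across the whole window that the protocol permits.

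The numbers are also small. The worst case of 5.5% is below the 10% loss to follow-up assumed in section 7, although it would come on top of ordinary dropout. The protocol names no primary time point, so most affected patients would still have a 6-week score. This too stands, and it is why no claim about power or bias is made.

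On the analysis periods, both blocks run to May, after 30 April, and may open with data cleaning and description. That largely stands: an early opening is not in itself an error, and only the final outcome analysis needs to wait.

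It can also be said that enrolment and surgery dates are not the same thing, since consent precedes surgery. That is correct. The 30 April limit rests on section 7, which dates surgery explicitly.

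Reading the end of collection as the end of recruitment does not help, because enrolment has its own line with its own end date.

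Finally, the 2021-only line is close to clerical, since the enrolment line in the same summary gives the longer period. That is fair, but the contradiction does not depend on any assumption about accrual.

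**Conclusion.** The concern holds. If surgery runs to the last date that section 7 permits, the final 6-week and 3-month visits fall 13 and 61 days after the latest reading of the stated end of collection. Under even accrual of 196 patients from 1 January 2021, between 0 and about 11 patients (0 to 5.5%) would lack a 3-month BCTQ, and at most about 2 (1.2%) would lack any postoperative BCTQ. The same patients would lack the matching grip-strength measurements. The counts depend on the assumed accrual pattern; the dates do not.

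This is an internal inconsistency of modest consequence that should be corrected. The 2021-only surgery line is a second, independent contradiction: one summary line is out of step with three other places that agree.

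**What to change.** - **Section 3, calendar:** set the end of data collection at the last surgery plus 3 months, which is 30 April 2024 at the latest.
- **Sections 3 and 9:** give the same analysis period in both, and state that the final outcome analysis starts after the last 3-month visit. Data cleaning and descriptive work may begin earlier.
- **Section 3, population line:** reconcile it with the enrolment line and with sections 7 and 9, so that one surgery window is stated throughout.

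The cost is protocol wording only, with no extra visits. The final analysis would start about one month after the April start in section 3, or about three months after the February opening in section 9. Dissemination by May 2024 may slip.

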4. BACKGROUND AND JUSTIFICATION OF THE STUDY

Surgical treatment for carpal tunnel syndrome consists of the transverse carpal ligament (LTC) section. The section of this ligament is usually done through a palmar skin incision. This technique is a common, simple, safe and effective procedure for the treatment of this pathology, but it is not exempt from complications such as the presence of painful palm scars, prolonged pain in the incision area, fatigue or weakness of the hand, periincisional pain (pillar pain) or prolonged convalescence time -return to previous activities⁻¹⁻³.

To try to minimize complications, percutaneous techniques have been developed. With these procedures, by not making an open incision through the palm, it is expected that the incidence of discomfort and tenderness in the palmar area will be reduced. In addition, it is also expected that there will be a decrease in postoperative morbidity, less time to return to work, and greater recovery of grip strength when this technique is used^{1,4-7}. However, its risk-benefit ratio compared to that of open release remains controversial⁸⁻¹². The risks to adjacent neurovascular structures inherent in these

percutaneous techniques remain one of the main factors preventing the acceptance of this technique^{4,13-15}.

To minimize these risks, ultrasound has been used as a guide when performing these percutaneous techniques, since ultrasound makes it possible to perfectly visualize carpal tunnel structures when performing this release^{1,12,16-18}. Ultrasound-guided percutaneous carpal tunnel release is a minimally invasive technique that has been developed over the last 20 years and has been shown to be effective and safe in several studies^{1,8,19-21}.

In our department, doctors from the Upper Limb Unit regularly use ultrasound for the diagnosis of upper limb pathology, as well as to perform local blocks when performing procedures under local anaesthesia. Due to the practice achieved with these procedures, ultrasound is being used as a support in other procedures such as the localization of foreign bodies, percutaneous release of CTS or the release of trigger fingers.

The aim of this study is to assess whether percutaneous release of the carpal tunnel guided by ultrasound provides, in our experience, more benefits than performing it through a short palmar incision.

5. HYPOTHESIS OF THE STUDY

Opening of the transverse carpal ligament percutaneously ultrasound-guided for the surgical treatment of carpal tunnel syndrome (CTS) has better results than opening by open surgery (palmar incision).

6. SPECIFIC AND SECONDARY OBJECTIVES OF THE STUDY

Main objective:

To analyze the functional results of the surgical treatment of CTS using percutaneous ultrasound-guided technique and to compare them with the results obtained by open surgery with a palmar incision.

Secondary objective:

To analyze the presence of complications (scar pain, pillar pain) and the pre- and postoperative difference in manual grip strength (measured with a JAMAR manual dynamometer) of surgical treatment of CTS using percutaneous ultrasound-guided technique and compare them with the results obtained by open surgery with a palmar incision.

7. DESIGN AND METHODS

Design:

Prospective observational cohort study.

Study population:

Patients in the CHUVI Health Area who have been diagnosed with CTS by a specialist in Orthopaedic Surgery and Traumatology at that centre, have undergone surgery for this pathology from 1 January 2021 to 31 January 2024, and meet the inclusion and exclusion criteria.

- Inclusion Criteria:

- 1.- Patient diagnosed with CTS by clinical examination and confirmed by complementary test (Electromyogram).
- 2.- Patients over 18 years of age.
- 3.- Patients who belong to the CHUVI Health Area.
- 4.- Patients with the capacity to consent and who agree to participate by signing the informed consent.
- 5.- Follow the guidelines and reviews set forth in the Consultation.

- Exclusion Criteria:

- 1- Patient who has previously undergone surgery for the same pathology in the same hand (recurrence).
- 2.- Patient incapacitated or unable to follow guidelines indicated by the Physician.
- 3.- Patient with associated pathology in the same hand for which he/she is going to be operated on in the same surgical act.
- 4- Patients with the presence of associated synovitis at the level of the flexor tendons of the hand to be treated.

- Sample size calculation.

Based on the study published by Kim et al²³, who studied the minimum clinically important difference (MCID) for the Boston Carpal Tunnel Syndrome Questionnaire²², and accepting an alpha risk of 0.05 and a beta risk of less than 0.2 in a bilateral contrast,

98 subjects in the first group and 98 in the second group are needed to detect a difference equal to or greater than 0.94 units. The common standard deviation is assumed to be 1. A follow-up loss rate of 10% has been estimated.

Procedure

Patients from the CHUVI Health Area diagnosed with the explained pathology, who meet the inclusion and exclusion criteria, and who are going to undergo surgery at the CHUVI by specialist doctors from the Orthopaedic Surgery and Traumatology Service belonging to the Upper Limb Unit, will be recruited. These patients will be informed of their pathology, and after signing the informed consent, surgery will be performed in the two proposed ways:

-Procedure A: ultrasound-guided percutaneous surgery.

-Procedure B: open surgery through a short palmar incision.

These two forms of surgical treatment are approved and used in our Service. The assignment to one or another surgical technique will be made based on the criteria of the physician who diagnoses the patient, as he or she does in his or her usual clinical practice, once the patient's clinical characteristics, pathology, and preferences have been heard.

Data will be collected from the patients included in the study in the preoperative consultation, intraoperatively and in the revision consultations that are usually carried out for this pathology 2 weeks after surgery, 6 weeks and 3 months.

In the preoperative consultation, the following will be collected:

- 1.- Grip strength of the hand measured with JAMAR manual dynamometer.
- 2.- Score of the specific questionnaire for the pathology of CTS: Boston Carpal Tunnel Syndrome Questionnaire²² (ANNEX 1).

Surgery will include:

- 1.- Time of surgical intervention
- 2.- Use or not of an ischemia cuff to perform surgery.

In the 2-week postoperative consultation, the following will be assessed:

- 1.- State of surgical wound.
- 2.- Presence of skin infection or other complication.
- 3.- Presence of pillar pain.
- 4.- Absence or presence of CTS (paresthesias or pain in the territory of the median nerve).

In the consultations that will be carried out 6 weeks and 3 months after surgery, the following will be assessed:

- 1.- Surgical incision status.
- 2.- Presence of skin infection or other complication.
- 3.- Presence of pillar pain.
- 4.- Absence or presence of CTS (paresthesias or pain in the territory of the median nerve)
- 5.- Grip strength of the hand measured with a JAMAR manual dynamometer.
- 6.- Score of the specific questionnaire for the pathology of CTS: Boston Carpal Tunnel Syndrome Questionnaire²² (ANNEX 1).

Data recording and management.

Potential candidates who meet the main characteristic of the study will be offered informed consent. Once the consent has been signed, a list of patients who meet the inclusion criteria and none of the exclusion criteria will be created.

The principal investigator ([name] [name]) will be responsible for the collection and custody of the data and will ensure that the pseudonymisation of the participants is maintained. These will be identified through a code in the CRD and in the electronic database, all their information being associated with this code and not with their personal data.

The other members of the team as third parties involved in the statistical analysis of the data will only have access to the coded information.

Statistical analysis.

A descriptive analysis of the data will be carried out, presenting the qualitative variables with their absolute frequency and percentage, and the quantitative variables with their mean and standard deviation (SD) or median and percentiles if they do not conform to a normal distribution.

Initially, a univariate analysis will be performed to determine which variables could have an independent effect on functional outcomes (grip strength, and the validated questionnaire for CTS: Boston Carpal Tunnel Syndrome Questionnaire ²²).

To compare quantitative variables between the two groups, to assess whether there are differences and whether they are significant, the normality of the distribution of the data in each of the cohorts will be analysed and the parametric t-student test or the

non-parametric test (Mann-Whitney U) will be applied. For the comparison of the qualitative variables between the two cohorts, the Chi-square test will be used.

Subsequently, including as independent variables those that show significance in the univariate analysis or are of clinical interest, they will be included in multivariate regression models.

The data will be analyzed with the SPSS 22.0 Software and 0.05 will be considered as the α accepted significance level for all hypothesis tests.

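### The stated sample-size inputs (difference 0.94, SD 1, two-sided 5%, beta below 0.2, 10% loss) require about 20 to 22 patients per group, not the 98 said to be needed

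*Protocol*

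**What the plan says.** The sample size calculation in section 7 (Design and methods) of the protocol gives a complete set of inputs.

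- Error rates: "accepting an alpha risk of 0.05 and a beta risk of less than 0.2 in a bilateral contrast".
- Target: "98 subjects in the first group and 98 in the second group are needed to detect a difference equal to or greater than 0.94 units". This calculation is based on a cited study of the minimum clinically important difference for the Boston questionnaire.
- Variability and attrition: "The common standard deviation is assumed to be 1. A follow-up loss rate of 10% has been estimated".

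The statistical analysis part of the same section compares the groups with Student's t-test or, if the data are not normal, says that the "non-parametric test (Mann-Whitney U) will be applied". The Summary (section 3) gives calendar dates for enrolment and adds "or until the calculated sample size is completed" as an alternative limit.

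The paragraph mentions no other allowance: nothing for multiplicity, clustering, confounder adjustment or unequal allocation.

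**The concern.** A difference of 0.94 with an SD of 1 is a standardised effect of 0.94, nearly one standard deviation. An effect of that size needs about twenty patients per group at 80% power, so 98 is far outside anything that rounding or choice of formula could explain.

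The inputs and the result cannot all belong to one calculation, and the reader cannot tell which figure is off. Two things depend on the answer. The sample-size paragraph is where the protocol says what difference between the techniques the study is meant to detect, and the figures do not confirm that this is 0.94. The calculated size is also one of the two limits on enrolment named in the Summary, so the number has a practical role.

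**Working it through.** **Inputs, all from the sample size calculation in section 7.** Difference d = 0.94; common SD = 1; alpha = 0.05, two-sided; beta = 0.2 as the limiting value, so power 80%; two equal groups; 10% loss. The test (t-test or Mann-Whitney) comes from the statistical analysis part of that section.

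**1. Attempt to reproduce 98.**

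Normal approximation: n = 2(z₀.₉₇₅ + z₀.₈₀)² × SD² / d² = 2(1.960 + 0.842)² / 0.94² = 17.8, so 18 per group. After loss: 18 / 0.9 = 20.

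t-test (noncentral t): n = 18.8, so 19 per group. After loss: 19 / 0.9 = 21.1, so 22.

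The total is 40 to 44 patients, against 196 stated. The ratio is 98/22 = 4.5 to 98/20 = 4.9. The stated figure is not reproduced.

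**2. Other readings of the stated inputs.** Beta is given as an inequality, so higher power is a permissible reading. The Mann-Whitney row takes the t-test value of 18.78 and divides it by 0.864, the lowest possible efficiency of that test relative to the t-test.

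| Reading | Evaluable per group | After 10% loss |
|---|---|---|
| t-test, 80% power | 18.8 → 19 | 22 |
| t-test, 90% power | 24.8 → 25 | 28 |
| t-test, 99% power | 42.6 → 43 | 48 |
| t-test, 99.9% power | 58.7 → 59 | 66 |
| Mann-Whitney, 80% power | 18.78 / 0.864 = 21.7 → 22 | 25 |

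A stricter alpha does not help either. By the normal approximation at 80% power, alpha 0.01 gives 27 (30 after loss) and alpha 0.001 gives 39 (44 after loss). No row comes near 98.

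**3. What 98 per group delivers at SD 1.** If 98 is the number enrolled, 98 × 0.9 = 88.2, so about 88 are evaluable. If 98 is already net of loss, 98 are evaluable. By the t-test:

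| Evaluable per group | Power for 0.94 | Detectable at 80% | Detectable at 90% |
|---|---|---|---|
| 88 | 99.999% | 0.425 | 0.49 |
| 98 | 99.9998% | 0.40 | 0.47 |

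**4. Working backwards.** By the normal approximation at 80% power, 88 evaluable per group fit a difference of 2.802 × √(2/88) = 0.42 at SD 1, or an SD of 0.94 / 0.422 = 2.2 at a difference of 0.94. With 98 evaluable the corresponding values are 0.40 and 2.35. These are back-calculations; the protocol states none of them.

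**The case against.** The strongest reply is that the discrepancy runs in the safe direction. Ninety-eight per group satisfies "a beta risk of less than 0.2", and on the stated inputs no test or conclusion is put at risk. The study is observational, both techniques are in routine use at the centre, and assignment and review visits follow usual practice, so extra patients face no added intervention. If the misreported figure were the SD (true value about 2.2) or the difference (true value about 0.42), 98 would still be roughly the right number. All of this stands, and it is why no change to enrolment is proposed. It does not rescue the paragraph, which says the number is needed rather than sufficient. The reassurance about power also holds only if 0.94 and SD 1 are the correct figures: at an SD of about 2.2, power for 0.94 is only about 80%.

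A second reply is that all the figures may be as intended, with an unreported margin for the planned multivariate models or for non-random assignment. That is possible, and so the conclusion should be that a figure is wrong or an input is missing. No such margin appears in the protocol, and the paragraph would still be incorrect as it reads.

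Third, the calculated size is only one of two enrolment limits, since the Summary also gives calendar dates. That is correct, and it limits the practical consequence without removing it.

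**Conclusion.** The sample-size paragraph is inconsistent with its own inputs. They require 18 to 19 evaluable and 20 to 22 enrolled patients per group, against 98 stated, a factor of 4.5 to 4.9. This assumes a two-group comparison of means with equal allocation, two-sided alpha 0.05 and 80% power, with loss applied as n / 0.9; the other readings tried leave a large gap. On the stated inputs the study has ample power for 0.94. What fails is the claim that 98 per group are required, and with it the reader's ability to tell what difference the study was sized for. The protocol alone does not show which figure is at fault, or whether an allowance went unreported. It also does not say whether 98 is before or after the 10% loss, although neither reading closes the gap. The paragraph needs correcting before the sample size is cited as justified.

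**What to change.** Retrieve the original calculation and reconcile the difference, the SD, the power and the number per group. Correct whichever is misreported, or state any allowance that was left out, and say where the 10% loss enters.

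If 98 per group with SD 1 is confirmed as the number enrolled, replace the claim with what that number delivers, for example:

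> With 88 evaluable patients per group (98 less 10% loss), two-sided alpha 0.05 and a common SD of 1, power is 80% for a difference of about 0.425, 90% for about 0.49, and above 99.9% for 0.94.

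If 98 turns out to be the evaluable number, use 0.40 and 0.47 for the 80% and 90% figures. If 0.94 survives the reconciliation, keep it as the benchmark for clinical relevance and report the between-group difference with its 95% confidence interval against it. The study could detect differences less than half that size, so statistical significance alone would not show that 0.94 had been reached.

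The cost is one paragraph of wording, after checking the original calculation. It needs no additional patients and no change to enrolment.

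### Technique is chosen on clinical grounds and preference, but only baseline BCTQ and grip strength are listed for collection, so residual confounding by indication is likely

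*Protocol*

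**What the plan says.** Section 7 of the Protocol (Design and Methods) describes a "Prospective observational cohort study". On allocation, the Procedure text states: "The assignment to one or another surgical technique will be made based on the criteria of the physician who diagnoses the patient". This follows usual practice and happens "once the patient's clinical characteristics, pathology, and preferences have been heard".

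The data schedule comes next. "In the preoperative consultation, the following will be collected" introduces two items: "Grip strength of the hand measured with JAMAR manual dynamometer" and "Score of the specific questionnaire for the pathology of CTS: Boston Carpal Tunnel Syndrome Questionnaire". The intraoperative items are operating time and "Use or not of an ischemia cuff to perform surgery". The remaining items belong to the visits at 2 weeks, 6 weeks and 3 months.

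The electromyogram appears only as an eligibility condition: "Patient diagnosed with CTS by clinical examination and confirmed by complementary test (Electromyogram"). Age likewise appears only as an inclusion criterion.

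The Statistical analysis text plans multivariate regression on variables that are significant in univariate analysis or clinically interesting. It names none.

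**The concern.** Section 5 hypothesises that the percutaneous technique gives better results, and section 6 makes the comparison with open surgery the main objective. The Protocol also says that allocation depends on patient features and preference. If any of those features affects recovery, the difference between cohorts mixes the effect of technique with the effect of who was selected for it. Regression can separate the two only for features that were recorded before surgery.

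This is a matter for the protocol, because a statistical analysis plan can choose covariates only from what was collected. Patient preference and the physician's reason exist at the consultation and are hard to reconstruct afterwards. Symptom duration may be hard to recover too.

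**Working it through.** **Step 1. Set the allocation rule against the data list.**

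| Factor that may influence the choice | Listed for preoperative collection? |
|---|---|
| Symptom and functional severity (BCTQ) | Yes |
| Grip strength | Yes |
| Electromyogram severity | No (confirmation is an eligibility condition) |
| Age | No (over 18 is an eligibility condition) |
| Sex, operated hand and dominance, occupation, comorbidity, symptom duration | No |
| Deciding physician | No |
| Patient preference, reason for the choice | No |

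The Protocol does not say which characteristics guide the choice. The rows answered No are reasonable candidates, not documented drivers. Operating time and cuff use arise after the technique is chosen, so they cannot serve as baseline confounders. Two listed baseline covariates remain for the multivariate models.

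**Step 2. Inputs from the Protocol (section 7, Sample size calculation).** 98 per group, SD 1, two-sided alpha 0.05, 10% loss to follow-up.

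The 98 does not follow from the stated 0.94 difference and SD 1: 2 × (1.96 + 0.842)² / 0.94² = 17.8, so 18 per group, and 18 / 0.9 = 20 with losses. That is a separate matter. It is noted here only because 98 is used below as the planned size.

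**Step 3. Smallest observed difference that is significant.**
- Evaluable per group: 98 × 0.9 = 88.2, about 88.
- Standard error: 1 × √(2/88) = 0.151.
- Threshold: 1.96 × 0.151 = 0.295 BCTQ units.

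**Step 4. Illustrative bias (assumed inputs, not in the Protocol).** Take one unrecorded binary prognostic factor and no true difference between techniques. Bias = difference in its share between cohorts × its effect on BCTQ.
- Low: 0.20 × 0.5 = 0.10.
- High: 0.40 × 1.0 = 0.40.

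**Step 5. Chance of a false significant result.** With b the bias and SE = 0.151, the probability is Φ(b/SE − 1.96) + Φ(−b/SE − 1.96).

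| Effect of factor | Difference in share | Bias | False-positive rate |
|---|---|---|---|
| 0.5 | 20 points | 0.10 | 10% |
| 0.5 | 40 points | 0.20 | 26% |
| 0.8 | 20 points | 0.16 | 19% |
| 0.8 | 40 points | 0.32 | 57% |
| 1.0 | 40 points | 0.40 | 76% |

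The nominal rate is 5%. All these figures are before adjustment. Adjusting for baseline BCTQ and grip would remove part of the bias, but the Protocol gives nothing from which to calculate how much.

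**The case against.** A reader might infer that the factors behind the choice are never recorded and that no later adjustment could make the cohorts comparable. The document does not support that reading, for four reasons.

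- Baseline BCTQ and grip are clinical characteristics, and they are recorded. The BCTQ in Annex 1 has 11 symptom items and 8 function items, so symptomatic and functional severity is measured before surgery and partial adjustment is possible.
- The preoperative list is not stated to be exhaustive, and the data collection form and database that the Protocol mentions are not shown. A plan to screen variables for their effect on outcome would sit more naturally with further patient data. The text supports only that the other factors are not listed for collection.
- Age and the electromyogram must be established for eligibility, so they may be retrievable from source records.
- The Protocol names no specific driver. It does not say that disease stage limits recovery at 3 months, or that advanced cases go to one technique. That mechanism is an assumption.

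The size can also be contested. The upper case needs a factor worth a full SD together with a 40-point imbalance. Even then the bias of 0.40 is 43% of the 0.94 units the study aims to detect (0.40 / 0.94). It could produce statistical significance, but not by itself a difference of the planned size.

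These points limit the wording and the claimed size. They do not remove the gap: allocation depends on patient features and preference, and only two baseline variables are listed to account for it.

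**Conclusion.** The point holds in this form: apart from BCTQ and grip strength, no factor that may drive the choice of technique is listed for preoperative collection. With the listed data the multivariate models can adjust for these two baseline variables only, so residual confounding by indication in the main comparison is likely.

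Its direction and size are unknown. The range of 0.10 to 0.40 BCTQ units rests on an assumed prognostic effect of 0.5 to 1.0 units and an assumed imbalance of 20 to 40 points, before any adjustment. The threshold of about 0.30 rests on the Protocol's own SD of 1 and about 88 evaluable patients per group. The upper part of the range would be enough to produce a significant result with no true difference. The issue should be corrected because it bears directly on the main objective and costs little to reduce.

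**What to change.** Extend the preoperative list in section 7 of the Protocol with:
- electromyogram severity, from the report already needed for eligibility;
- symptom duration;
- age and sex;
- operated hand and dominance;
- occupation;
- diabetes and other relevant comorbidity;
- the deciding physician (coded);
- the main reason for choosing the technique, including patient preference.

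State that these, with baseline BCTQ and grip, are used in the adjusted comparison of techniques. Their coding and the form of the model can be left to the statistical analysis plan.

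For patients already enrolled, abstract the retrievable items from source records and report the remaining confounding as a limitation.

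No new test or visit is needed, and how the technique is chosen does not change. The cost is a little more data entry and one protocol modification, which section 8 requires to be sent for ethics re-evaluation.
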